Dapagliflozin which was originally developed to control blood glucose level in patients with diabetes has recently been shown to have beneficial effects on both the heart and kidney.

Importantly, a large clinical trial has shown dapagliflozin reduced kidney problems. From the way we think the pills work, there is good reason to believe this new medication could benefit people who have kidney disease even they are not diabetic.

To date, there hasn't been a trial that studied the effect of dapagliflozin in terms of anemia improvement only on non-diabetic CKD.

Objectives

The main objective of this study is to:

- Compare use of SGLT2i versus placebo and standard care in regression of chronic kidney disease in non-diabetic CKD patients.
- Study the effect of SGLT2i in decreasing the risk of anemia and improving anemia in non-diabetic CKD patients.
- Study the impact of SGLT2i regarding cardiovascular system.

Hypothesis

Additional therapies to slow kidney function decline are highly desired. The DAPA-CKD trial demonstrated that the sodium glucose co-transporter 2 inhibitor dapagliflozin significantly reduced the risk of kidney failure and prolonged survival in participants with chronic kidney disease with and without type 2 diabetes.

Patients and methods

Study sitting: Urology and Nephrology Center, Mansoura University.

Study design and sample size:

- **Sample size:** was calculated based on previous research by (DAPA-CKD) by (Heerspink et al., 2020) using G. power program with α error 0.05 and power 80% and it was equal to approximately 98 patients.

Type of the study: Randomized controlled trial.

Patients' enrollment: 100 patients with non-diabetic CKD with an estimated glomerular filtration rate (eGFR) of 20-75 ml/min/1.73m² will be randomized into 2 equal groups:

- **Study group:** 50 patients will receive SGLT2i as add on drug, Dapagliflozin 10 mg will be used once daily with or without food.
- **Control group:** 50 patients will receive placebo beside the conventional medications.

All patients will be followed-up for 12 months and their results will be interpreted.

Inclusion criteria:

1. Non-diabetic CKD patients aged more than 18 years.
2. Patient with eGFR > 20 ml/min/1.73m² by 2021 CKD-EPI creatinine equation

Exclusion criteria:

1. eGFR < 20 ml/min per 1.73 m².
2. Medical history of chronic disease (diabetes mellitus, chronic liver disease, bladder cancer, severe respiratory distress).

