- Serum hepcidin level
- Serum erythropoietin level.

➤ **Cardiovascular investigatory tools:**

- Electrocardiography (ECG).
- Echocardiography to assess myocardial function.

➤ **Radiological investigations:**

- Agatston score using CT scan: for assessment of coronary calcification.

Outcomes:

Primary outcome measures:

- Time to the first occurrence of any of the components of the composite:
≥50% sustained decline in eGFR, reaching end-stage kidney disease.
[Time Frame: 12 months]

Secondary outcome measures:

- Effect of Dapagliflozin on eGFR.
- Effect of Dapagliflozin on anemia & erythropoietin level.
- Effect of Dapagliflozin on myocardial function and coronary calcifications.
- Safety of Dapagliflozin regarding the number of hypoglycemia episodes between groups and serious adverse events.

Statistical Analysis:

Qualitative data will be displayed in cross tabulations, and quantitative data will be described in terms of arithmetic mean \pm SD. Bivariate techniques will be used for initial evaluation of contrasts. Thus, the chi-square and Fisher's exact tests will be used for comparisons of frequencies of qualitative variables; the Mann-Whitney test and the unpaired t-test will be used for comparisons of means of two quantitative variables. A p-value ≤ 0.05 is considered significant. Patient survival rates will be assessed using the Kaplan-Meier method. All analyses will be carried out using the computer package SPSS for windows, release 21 SPSS Inc. Chicago, III, USA.

Administrative design

All the patients provided written informed consent before study entry and the approval was obtained from institutional review board (MS.22.04.1973) in Faculty of Medicine, Mansoura University. There is no funding.

References

1. Eckardt, K. U., Coresh, J., Devuyst, O., Johnson, R. J., Köttgen, A., Levey, A. S., & Levin, A. (2013). Evolving importance of kidney disease: from subspecialty to global health burden. *The Lancet*, 382(9887), 158-169.
3. Silver, S. A., Bell, C. M., Chertow, G. M., Shah, P. S., Shojania, K., Wald, R., & Harel, Z. (2017). Effectiveness of quality improvement strategies for the management of CKD: a meta-analysis. *Clinical Journal of the American Society of Nephrology*, 12(10), 1601-1614.

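### Secondary quantitative outcomes get mean ± SD and an unadjusted t-test or Mann-Whitney test, with no rule for choosing and no use of baseline values

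*Combined protocol and SAP*

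**What the plan says.** The Statistical Analysis section has one rule for summaries: "quantitative data will be described in terms of arithmetic mean" together with the SD. It mentions no median, interquartile range, geometric mean or transformation. For comparing arms it says that "the Mann-Whitney test and the unpaired t-test will be used for comparisons of means of two quantitative variables". No variable list, distribution check or other rule decides between the two tests, and the Mann-Whitney test does not in fact compare means. These bivariate methods are presented as a first look, but no later model for quantitative outcomes follows. The threshold is that "A p-value ≤ 0.05 is considered significant", with sidedness not stated.

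The lists of baseline and post-intervention investigations show ferritin, hepcidin, erythropoietin, urine protein, haemoglobin, haematocrit and MCV at both baseline and 12 months, along with serum creatinine, from which eGFR follows. The imaging item "Agatston score using CT scan: for assessment of coronary calcification" also appears at both times. BNP appears in the baseline list only. The secondary outcomes name eGFR, anaemia and erythropoietin, myocardial function and coronary calcification. The primary outcome is a time-to-event composite.

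**The concern.** Concentrations such as ferritin, hepcidin and erythropoietin, and urine protein, cannot be negative and often have a long upper tail. The Agatston score can also be exactly zero. For such variables a mean ± SD need not describe a typical patient, and a few large values can dominate a t-test on the raw scale.

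Two further problems do not depend on skew. With no rule for choosing, the test can be picked after both p-values are known. And an unadjusted comparison at 12 months discards the patient's own starting value, which is often the best predictor of the final value. With 50 patients per arm that information matters. At stake are the precision and credibility of the secondary anaemia and cardiovascular comparisons.

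**Working it through.** **Inputs from the documents.** Arms: patients "will be randomized into 2 equal groups", 50 each. Follow-up: "All patients will be followed-up for 12 months". Significance level 0.05, taken as two-sided. The documents give no distribution, SD or correlation for any of these variables, so those inputs are assumed and shown as ranges.

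**The plan's own figure.** The sample size was found "using G. power program with α error 0.05 and power 80"%, and "it was equal to approximately 98 patients". No effect size or outcome is given, so it cannot be reproduced. Solved backwards for 49 per arm, d = √(2/49) × (1.960 + 0.842) = 0.566 (0.572 by exact t). Nothing ties it to the variables considered here.

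**Step 1: summaries under an assumed lognormal.** With log-SD s, mean/median = exp(s²/2) and SD/mean = √(exp(s²) − 1).
- s = 0.5: mean/median 1.13, SD/mean 0.53.
- s = 1.0: mean/median 1.65, SD/mean 1.31. With median 1, mean − SD = 1.65 − 2.16 = −0.51, an impossible value.
- SD exceeds the mean once s is above about 0.83.

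**Step 2: cost of skew alone, no baseline.** At 50 per arm an effect of 0.566 log-SD gives a log-scale t-test 80% power. From 10,000 simulated trials per setting:

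| log-SD | raw t-test | Mann-Whitney | raw t-test: points below 80% |
|---|---|---|---|
| 0.3 | 79% | 78% | 1 |
| 0.5 | 75% | 78% | 5 |
| 0.8 | 68% | 78% | 12 |
| 1.0 | 62% | 78% | 18 |
| 1.2 | 55% | 78% | 25 |

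Mann-Whitney loses about 2 points throughout.

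**Step 3: cost of ignoring baseline.** With baseline correlation r on the log scale, ANCOVA reduces the residual SD by the factor √(1 − r²). The effect that gives ANCOVA about 80% power is therefore 0.566 × √(1 − r²) log-SD. For an unadjusted log-scale t-test at that effect, approximate power is Φ(d × √(50/2) − 1.96):
- r = 0.3: d = 0.540, Φ(0.74) = 77% (exact t 76%).
- r = 0.5: d = 0.490, Φ(0.49) = 69% (exact t 68%).
- r = 0.7: d = 0.404, Φ(0.06) = 52% (exact t 52%).

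Simulated power at the same effects, log-SD 0.5 to 1.2:

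| r | log-scale ANCOVA | Mann-Whitney | raw t-test |
|---|---|---|---|
| 0.3 | about 80% | 73-75% | 51-71% |
| 0.5 | about 80% | 65-67% | 43-62% |
| 0.7 | about 80% | 48-51% | 32-46% |

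Taking Mann-Whitney as 74%, 65% and 50%, its shortfall from 80% is 6, 15 and 30 points. Of these, 80 − 76 = 4, 80 − 68 = 12 and 80 − 52 = 28 points come from leaving out baseline. The rest, 2 to 3 points, comes from using ranks.

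**Step 4: type I error under no effect.** The raw t-test rejected in 2.9-5.3% of null trials. Running both tests and keeping either significant result rejected in 6.3-7.8%.

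**Step 5: an Agatston-like score.** Assume 30-50% zeros, with log-SD 1.2-1.5 among positive values. At 40% zeros and log-SD 1.2 (median 100 among positive values), the mean is about 123, the SD about 300 and the median about 32. For an effect that halves positive values and adds 10 points of zeros, power is 24-51% for the raw t-test, 30-55% for Mann-Whitney and 34-49% for a t-test on log(1 + score). None of the three is best in every setting.

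**The case against.** The strongest reply is that the plan already names the Mann-Whitney test, which is valid under skew and within about 2 points of the unadjusted log-scale t-test. That is correct. A reader might infer that skew and mean ± SD alone reduce power from about 80% to 50% or less. The working does not support this: at baseline correlation 0.7, 28 of the 30 points that Mann-Whitney loses come from leaving out baseline. But the reply does not rescue the plan. Nothing commits it to Mann-Whitney, and that test is also unadjusted.

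Several other objections stand.
- The degree of skew is assumed. At log-SD 0.3-0.5 the raw t-test loses only 1-5 points.
- The raw t-test's type I error is not inflated, so the test is inefficient here rather than invalid.
- Mann-Whitney can be accompanied by an effect estimate such as the Hodges-Lehmann shift. The gap is that the plan names none.
- A reader might infer that two of the three main objectives rest on skewed variables. Haemoglobin and haematocrit bear directly on anaemia and need not be skewed. The cardiac outcome includes myocardial function. Proteinuria is measured but is not a named outcome.
- A reader might count BNP as a 12-month comparison. No follow-up BNP is listed, so only its baseline summary is in question.
- A log(score + 1) analysis is not shown to be better for the Agatston score.

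**Conclusion.** The concern holds for secondary variables; the primary time-to-event outcome is untouched. Mean ± SD is the only planned summary, the choice of test is open, and the planned tests ignore baseline.

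For an assumed lognormal outcome, baseline adjustment on the log scale gains about 6, 15 and 30 points of power over Mann-Whitney at baseline correlations 0.3, 0.5 and 0.7, and more over the raw t-test. Skew by itself costs the raw t-test 1-5 points if mild (log-SD 0.3-0.5) and 12-25 points if marked (0.8-1.2). Choosing between the tests after seeing both results would put type I error at about 6-8% per variable. These sizes rest on assumed distributions and correlations. That the choice of test is open and baseline goes unused can be read directly from the plan. The change is worth making because it is nearly free.

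**What to change.** Before analysis, name one summary and one test for each secondary variable:
- **Ferritin, hepcidin, erythropoietin, proteinuria:** median (IQR). Compare arms at 12 months by ANCOVA on the log scale, adjusted for log baseline, and report the geometric-mean ratio with 95% CI.
- **Haemoglobin, haematocrit, MCV, eGFR:** keep mean ± SD. Compare by raw-scale ANCOVA adjusted for baseline.
- **Agatston score:** proportion at zero plus median (IQR), with one prespecified rank-based or two-part comparison.
- **BNP:** change only the baseline summary, to median (IQR).

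Remove the open choice between the t-test and Mann-Whitney for these variables, and the description of Mann-Whitney as a comparison of means.

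The cost is SAP wording. No extra patients, visits or assays are needed, and the same software can run the models. For the four log-scale variables, the effect is reported as a ratio rather than a difference in means. The stated sample size does not change, since it is not tied to any of these variables.

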3. Evidence of urinary obstruction or difficulty in voiding at screening.
4. Receiving high dose diuretics or combined ACEI and ARB.
5. History of recurrent urinary tract infection.

6. Active infection including TB and HIV.
7. Current or previous organ transplantation or expected to get a kidney transplant within 12 months.
8. Patients who are on SGLT2i for more than the preceding 3 months.

Study design:

Study Protocol:

- Patients included in the study will be treated with dapagliflozin initiated at a single daily morning dosage of 10 mg/day.

Methods:

The following data will be collected and evaluated for all patients:

I-Baseline investigations:

- Patients of both groups will be subjected to full history taking including duration of CKD and drug history and routine clinical examination.
- Ankle/brachial pressure index (ABPI) to assess peripheral vascular disease.

➤ Laboratory investigations:

- 1) Serum creatinine, Creatinine clearance.
- 2) Urine analysis.
- 3) 24-hour urine protein and/or spot urine protein/creatinine ratio.
- 4) Random blood glucose.
- 5) Lipid profile
- 6) Iron profile tests:

- Hemoglobin
- Mean corpuscular volume (MCV) and Hematocrit (Hct).
- Serum ferritin
- Transferrin saturation (TSAT)
- Serum hepcidin level
- Serum erythropoietin level.

7) B-type natriuretic peptide (BNP) level.

➤ **Cardiovascular investigatory tools:**

- Electrocardiography (ECG).
- Echocardiography to assess myocardial function.

➤ **Radiological investigations:**

- Agatston score using CT scan: for assessment of coronary calcification.

1. II-Post-intervention investigations:

All patients will be evaluated every visit (every 3 months) regarding:

- Regular measurement of blood pressure each visit.
- Ankle/brachial pressure index.
- Laboratory investigations:
 - 1) Serum creatinine, creatinine clearance.
 - 2) Urine analysis.
 - 3) 24-hour urine protein and/or spot urine protein/creatinine ratio.
 - 4) Fasting blood glucose.
 - 5) Lipid profile.

6) Iron profile (Hemoglobin, MCV, hematocrit, ferritin, TSAT,)

All patients will be evaluated at 12 months regarding:

➤ Ankle/brachial pressure index.

➤ **Laboratory investigations:**

1) Serum creatinine, Creatinine clearance.

2) 24-hour urine protein and/or spot urine protein/creatinine ratio.

3) Urine analysis.

4) Fasting blood glucose.

5) Lipid profile.

6) Iron profile tests:

- Hemoglobin
- Mean corpuscular volume (MCV) and Hematocrit (Hct).
- Serum ferritin
- Transferrin saturation (TSAT)

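### Continuous secondary outcomes get only unadjusted two-sample tests, with no stated role for the baseline values and no choice between month-12 value and change

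*Combined protocol and SAP*

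**What the plan says.** In the combined protocol and SAP, the Outcomes section words the secondary efficacy outcomes as "Effect of Dapagliflozin on eGFR", "Effect of Dapagliflozin on anemia & erythropoietin level" and "Effect of Dapagliflozin on myocardial function and coronary calcifications". eGFR and erythropoietin are thus named, and Methods measures coronary calcification by the Agatston CT score. Anaemia has no chosen variable, although haemoglobin, MCV, haematocrit, ferritin, TSAT and hepcidin are all collected. Myocardial function has an instrument, echocardiography, but no parameter. One item under Objectives is to "Study the effect of SGLT2i in decreasing the risk of anemia and improving anemia in non-diabetic CKD patients", which fits either a yes/no or a continuous outcome.

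Methods takes baseline measurements in both groups. Follow-up is quarterly ("All patients will be evaluated every visit (every 3 months) regarding") for creatinine and the main iron indices. Erythropoietin, echocardiography and the Agatston score are repeated only at 12 months. A 12-month time frame is printed against the primary outcome but not against the secondary ones.

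The Statistical Analysis section opens its comparisons with "Bivariate techniques will be used for initial evaluation of contrasts" and continues, for quantitative data, "the Mann-Whitney test and the unpaired t-test will be used for comparisons of means of two quantitative variables". It gives no rule for choosing between the two tests, names no covariate, and does not choose between value and change. The other methods named are chi-square and Fisher tests for frequencies and Kaplan-Meier for survival.

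**The concern.** Anaemia and the cardiovascular system are the two subjects in the trial's title, so these outcomes carry much of what the trial is for. With 50 patients per arm, precision is scarce, and a baseline measurement that has already been paid for is the cheapest source of more. The plan does not say that it will be used.

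The unstated metric adds a second problem. A test on month-12 values and a test on changes are different tests of the same hypothesis and can disagree. If the choice between them is made after the data are seen, the nominal 5% level no longer holds for that outcome.

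**Working it through.** **Inputs from the documents.** 100 patients in two equal groups (50 per arm); significance at p ≤ 0.05; 80% power, which is stated for the overall sample size. The plan's only design figure, about 98 patients, comes without an effect size, SD or event rate and is not tied to any secondary outcome. It cannot be reproduced forward, and nothing below depends on it.

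**Assumptions.** Two-sided test, normal data, equal SD at baseline and month 12, all 50 per arm complete, and baseline-to-month-12 correlation rho from 0.3 to 0.9. The documents give no rho.

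**Precision.** The normal approximation for month-12 values is (1.960 + 0.842) × sqrt(2/50) = 0.56 SD; the noncentral t gives d = 0.566 SD. Relative to month-12 values, the variance is 2(1 − rho) for changes and 1 − rho² for ANCOVA, so the detectable differences are d × sqrt(2(1 − rho)) and d × sqrt(1 − rho²). For rho = 0.7: 0.566 × sqrt(0.60) = 0.438 and 0.566 × sqrt(0.51) = 0.404.

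| rho | Values (SD) | Changes (SD) | ANCOVA (SD) | Patients, values ÷ ANCOVA: 1/(1 − rho²) | Patients, changes ÷ ANCOVA: 2/(1 + rho) |
|---|---|---|---|---|---|
| 0.3 | 0.57 | 0.67 | 0.54 | 1.10 | 1.54 |
| 0.5 | 0.57 | 0.57 | 0.49 | 1.33 | 1.33 |
| 0.7 | 0.57 | 0.44 | 0.40 | 1.96 | 1.18 |
| 0.9 | 0.57 | 0.25 | 0.25 | 5.26 | 1.05 |

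Apart from one degree of freedom, which does not alter d to three decimals, ANCOVA is at least as precise as either unadjusted reading throughout. With 45 or 40 complete patients per arm the figures are 0.60 or 0.63 SD on values and, at rho 0.7, 0.46 or 0.49 SD on changes and 0.43 or 0.45 SD with ANCOVA.

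**Open choice.** Under the null, the statistics for value and change correlate at (1 − rho)/sqrt(2(1 − rho)) = sqrt((1 − rho)/2). The chance that at least one is significant at 5%, from the bivariate normal, is 8.8%, 9.1%, 9.4% and 9.6% at rho 0.3, 0.5, 0.7 and 0.9. Two independent tests would give 1 − 0.95² = 9.75%, so these values are near the limit for two tests. Simulation with 50 per arm (40,000 runs) gives 8.8%, 9.2%, 9.3% and 9.4%. In the same simulations:
- free choice of t-test or Mann-Whitney test on values: 5.8 to 6.1%;
- free choice among all four combinations: 10.5 to 11.5%;
- ANCOVA alone: 4.9 to 5.1%.

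For eGFR or haemoglobin, taking the best of value or change at any of the four quarterly visits (eight tests) gives 19 to 27%, for rho 0.5 to 0.9 and two assumed correlation patterns.

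**The case against.** Both named tests are valid in a randomised comparison, and the outcomes are secondary with no stated multiplicity control, so 5% is at most a per-test level. That stands: a reader might infer that the planned tests are wrong, and they are not.

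A reader might also infer that baseline is ignored. The documents do not support this. The aim of improving anaemia, together with paired baseline and 12-month measurements, makes change from baseline a natural reading, and an unpaired t-test on changes uses baseline. The supportable statement is that no role is stated. If changes were intended and rho is 0.7 or more, ANCOVA adds little.

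The 19 to 27% figure should not be read as the expected error rate. It supposes that the best of eight tests is reported. The plan says "All patients will be followed-up for 12 months and their results will be interpreted" and schedules a separate 12-month evaluation, so month 12 is the likely endpoint even though it is not stated for these outcomes. Nothing in the documents suggests result-driven selection. The choice between the t-test and the Mann-Whitney test alone costs about one percentage point, and the usual division by normal or skewed data is an obvious reading.

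Finally, the precision figures assume normality and do not carry over directly to erythropoietin or the Agatston score if these are skewed. For the Agatston score a rank-based lead analysis is at least as defensible as a log scale, because with many zeros the result depends on the constant that is added.

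**Conclusion.** The point holds as one about precision and an analysis left open, and should be addressed. The plan names only unadjusted tests, describes no later arm comparison, and leaves value versus change unstated. A baseline-adjusted analysis is at least as precise as either reading. At an assumed rho of 0.7 it is worth 1.96 times the patients against month-12 values but only 1.18 times against changes; the largest gain, 5.26 times, arises only at rho 0.9 and only if raw values were intended. The relevant error figure is about 9% per outcome if the metric is chosen after the data are seen; 19 to 27% is a hypothetical ceiling.

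A reader might infer that every secondary variable is undefined. That goes too far: eGFR, erythropoietin and the Agatston score are identified, and only anaemia and myocardial function lack a variable. All sizes rest on assumed correlations, roughly normal data and 50 complete patients per arm.

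**What to change.** - **Lead analysis.** For each continuous secondary outcome, use ANCOVA of the month-12 value on arm and baseline value. For the quarterly measures, eGFR and haemoglobin, a baseline-adjusted mixed model with the month-12 contrast is an equal alternative; state which one in advance.
- **Variables.** Name one anaemia variable (for example haemoglobin) and one echocardiographic variable. If a yes/no anaemia outcome is also wanted, define it separately and use the chi-square or Fisher test already planned.
- **Scale, fixed beforehand.** For example untransformed for eGFR and haemoglobin, and log for erythropoietin. For the Agatston score, use a baseline-adjusted rank-based analysis or log(score + 1), with the choice written down before the data are seen.
- **Sensitivity analyses.** Keep the t-test and the Mann-Whitney test here.

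The cost is SAP wording, one degree of freedom, and the need for a baseline value for each patient. No new visits, measurements or patients are required. ANCOVA needs a month-12 value, as the current tests would at that time point. A scale that fits poorly is then handled by the sensitivity analyses, not by switching the lead analysis.

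### Haemoglobin and four other blood indices are measured at four post-baseline visits, but the plan names only one-value-per-patient tests and gives no time point or missing-data rule for the anaemia outcome

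*Combined protocol and SAP*

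**What the plan says.** Under Methods, II-Post-intervention investigations, the protocol states "All patients will be evaluated every visit (every 3 months) regarding" a list whose sixth laboratory item is "Iron profile (Hemoglobin, MCV, hematocrit, ferritin, TSAT". Follow-up is 12 months, so each patient who stays has values at months 3, 6, 9 and 12. Hepcidin and erythropoietin are not on the 3-monthly list. They appear only at baseline and at 12 months.

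Under Outcomes, the relevant secondary measure reads, in full, "Effect of Dapagliflozin on anemia & erythropoietin level". It names no variable, threshold or time point.

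Under Statistical Analysis, the between-arm methods for quantitative variables are given in one clause: "the Mann-Whitney test and the unpaired t-test will be used for comparisons of means of two quantitative variables". The threshold is "A p-value ≤ 0.05 is considered significant", with no rule for multiple tests. The section describes its bivariate methods as a first evaluation but names no later step. It contains no repeated-measures method, baseline adjustment, missing-data rule or analysis set. The only method that involves time is Kaplan-Meier, and it is stated for patient survival.

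**The concern.** The unpaired t-test and the Mann-Whitney test each take one value per patient. Applied to an index measured four times after baseline, they leave the analyst to decide which value to use, and the plan does not make that choice.

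The two obvious choices each have a cost:

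- **One test at month 12.** Three of the four values play no part, and a patient who leaves after month 3, 6 or 9 contributes nothing. If patients with low haemoglobin are likelier to leave, those who remain give a biased comparison.
- **One test at each visit.** All values are used, but there are four chances per index to cross 0.05.

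Because neither is fixed in advance, the choice could be made after the results are seen. Anaemia is in the trial's title, and the Rationale gives it as the gap in evidence that the trial is meant to fill.

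**Working it through.** **The plan's own figure.** The sample size "was calculated based on previous research by (DAPA-CKD) by" the cited authors, "using G. power program with α error 0.05 and power 80% and it was equal to approximately 98 patients". No effect size, SD or event rate is given, so 98 cannot be reproduced or refuted. Solved backwards for two means with 49 per arm, d = (1.960 + 0.842) × √(2/49) = 0.566 two-sided, or 0.502 one-sided. Nothing ties either value to haemoglobin, and the point does not depend on it.

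**Inputs from the documents.** 100 patients "will be randomized into 2 equal groups", so 50 per arm; four post-baseline visits; threshold 0.05.

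**Inputs assumed (not in the documents).** Haemoglobin SD 1.5 g/dL; true difference 0.7 g/dL; equal correlation r between any two visits, baseline included, from 0.5 to 0.8; two-sided testing.

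**Step 1: values left out by a single month-12 test.** Per arm, 50 × 4 = 200 post-baseline values, of which 50 × 3 = 150 are not used.

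**Step 2: false positives if each visit is tested.** Four independent tests would give 1 − 0.95⁴ = 18.5%. For correlated visits with no true effect, simulation gives about 15.5% at r = 0.5 and about 11% at r = 0.8, for each index.

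**Step 3: power with complete data.** The standard error of the arm difference is 1.5 × √(2f/50) = 0.300 × √f, where f is the variance relative to one unadjusted visit. Power is from the t-test formula with difference 0.7.

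| Analysis | f | f at r = 0.5 / 0.8 | SE (g/dL) | Power |
|---|---|---|---|---|
| Month 12, unadjusted | 1 | 1 / 1 | 0.300 / 0.300 | 64% / 64% |
| Month 12, baseline-adjusted | 1 − r² | 0.75 / 0.36 | 0.260 / 0.180 | 76% / 97% |
| Mean of four visits, unadjusted | (1 + 3r)/4 | 0.625 / 0.85 | 0.237 / 0.277 | 83% / 71% |

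Averaging therefore cuts the variance by 1 − 0.625 = 38% down to 1 − 0.85 = 15%. That gain belongs to the average, not to the month-12 contrast, and it assumes the full effect is present from month 3.

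**Step 4: what the repeated-measures part adds at month 12.** With complete data and the same baseline adjustment it adds essentially nothing. With 10–20% dropout, spread evenly over visits, it adds 0 to 2 points of power over a baseline-adjusted analysis of completers. For example, with a true effect of 0.566 SD and 20% dropout, power goes from 83.2% to 84.2% (equal correlation 0.5), or from 84.3% to 86.5% (correlation 0.85 between adjacent visits, falling with distance).

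**Step 5: bias.** With about 10–12% lost by month 12, likelier after a low observed haemoglobin, simulations gave month-12 completer estimates of 0.65–0.68 g/dL against a true 0.70. The all-visit likelihood estimate was 0.69–0.71. The shortfall is about 0.02 (0.70 − 0.68) to 0.06 (0.71 − 0.65) g/dL. Another loss rule of the same kind gave completer estimates of 0.63–0.65, so the size depends on how leaving is related to haemoglobin.

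**The case against.** A reader might infer that the plan discards three of the four post-baseline values and drops early leavers. The documents do not say so. They name no time point for the anaemia comparison and are silent on missing data. Visit-by-visit tests would use every value and would count a leaver at each visit attended. A t-test on each patient's mean over visits, or a chi-square test on anaemia at any visit, also fits the named methods. This objection stands: the loss is conditional on a single month-12 test, and the defect is the missing specification.

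A reader might also credit the repeated-measures model with a large gain in power. That too is unsupported. With complete data, the model has no advantage at month 12 over a baseline-adjusted comparison, and steps 3 and 4 show that the gain there comes nearly all from the baseline term. A bias of 0.06 g/dL is 0.06/0.30 = one-fifth of the standard error of an unadjusted comparison. The loss rule in step 5 depends on observed values, which is the situation in which a likelihood model does well. These limits stand, and they make the benefit of using all visits modest.

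Two further limits apply. The point covers the five indices on the 3-monthly list, not hepcidin or erythropoietin. And although anaemia is in the title, it comes after the cardiovascular system there; it is the second aim and a secondary outcome.

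None of this supplies the missing time point, missing-data rule or handling of repeated values.

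**Conclusion.** The point holds in conditional form. The schedule yields four post-baseline values of five indices, and the plan does not say how the anaemia comparison will use them. One month-12 test would lose 150 of 200 values per arm and all patients who leave before month 12. Separate tests at each visit would carry about an 11% to 15.5% chance of a false positive per index, on an assumed correlation of 0.8 to 0.5.

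The recommended analysis raises power for the month-12 haemoglobin contrast from about 64% to 76–97%. This rests on the assumed SD, difference and correlation, and in particular on baseline and month 12 being correlated at 0.5 to 0.8; if correlation fades over the year, the gain is smaller. What the extra visits add at month 12 is protection from a small bias of about 0.02–0.06 g/dL, provided that leaving depends on recorded values. The plan should be changed on this point, but it concerns a secondary outcome and does not undermine the trial.

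**What to change.** In the Statistical Analysis section, replace the unpaired tests for these indices with text to this effect:

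> Haemoglobin will be analysed with one mixed model for repeated measures using all values at months 3, 6, 9 and 12, with arm, visit, arm-by-visit interaction and the baseline value as terms. The haemoglobin result is the difference between arms at month 12, with its 95% confidence interval. The average difference over months 3 to 12 is supportive. Visits will not be tested separately. The model assumes that missing values are missing at random. Haematocrit, TSAT and log-transformed ferritin will be analysed in the same way.

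In Outcomes, name haemoglobin at month 12 as the anaemia variable and time point. Hepcidin and erythropoietin stay outside this model, since each has only one post-baseline value.

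The average is kept supportive because it would dilute an effect that builds up slowly. A short sensitivity analysis of the missing-at-random assumption would be sensible, since the documents give no expected dropout.

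Cost: SAP wording and slightly more analysis work, with no new visits, samples or patients. The price is reliance on the missing-at-random assumption, which the data cannot confirm.
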